6.12. End of Study/End of Follow-up

The date the subject met criteria for study discontinuation and the reason for study discontinuation will be recorded.

7. STUDY ASSESSMENTS

7.1. Screening/Baseline Assessments

Only subjects who meet all inclusion and exclusion criteria specified in Section 4 will be enrolled in this study. Assessments will begin after obtaining a signed informed consent from the subject.

Subject medical history includes a thorough review of significant past medical history, current conditions, any treatment for prior malignancies and response to prior treatment, and any concomitant medications. The number of prior lines of therapy will be determined using the criteria established by Rajkumar et al. ([Rajkumar 2015](#)). In brief:

- If a treatment regimen is discontinued for any reason and a different treatment regimen is started, it is considered a new line of therapy
- A new line of therapy is also considered to start when an unplanned substitution or addition of 1 or more drugs is made to an existing course of therapy for any reason
- In subjects undergoing >1 ASCT (except in the case of a planned tandem ASCT), each transplant that follows the first one should be considered a new line of therapy
- A planned course of therapy that has multiple phases, such as induction therapy followed by the first ASCT and maintenance therapy, is considered to be a single line of therapy.

A baseline plasmacytoma scan, per institutional standard imaging modality, is conducted during screening only in cases of suspected or known plasmacytoma. During treatment, plasmacytoma evaluations can be performed at any time to confirm a response of PR or better, or as clinically indicated to confirm PD.

BM aspirate (including a BM aspirate clot) and biopsy are required as part of the baseline visit ([Appendix A](#) and Section 7.2).

Physical examinations should include assessments of the following body parts/systems: abdomen, extremities, head, heart, lungs, neck, and neurological. Weight and height will also be measured; measurements of height obtained within the prior 12 months may be utilized (Section 7.7.12).

Blood and urine tests will include CBC with differential, serum chemistry panel, serology (hepatitis B and C), PT/PTT/INR, HbA1c (for subjects in Part C) and urinalysis. A pregnancy test will be conducted for subjects of childbearing potential (Section 4.3). Urinalysis with microscopy is required if urinalysis results are abnormal; UPCR calculation is also required. Further details of these tests are provided in Section 7.7.11.

Blood samples will be collected for pharmacodynamic biomarker assessments by the central laboratory.

7.2. Response/Efficacy Assessments

Response assessment includes SPEP/immunofixation, UPEP/immunofixation (in subjects with a baseline urine M-protein ≥ 200 mg/24 hour or for assessment of VGPR or better), SFLC, quantitative immunoglobulins, and plasmacytoma evaluation, per institutional standard imaging

modality (at baseline, every 4 cycles, and at additional timepoints if clinically indicated). These samples will be collected for local assessment at the times provided in [Appendix A](#). In addition, blood will be analyzed in the central laboratory using a modified SPEP for subjects with IgG myeloma.

BM aspirate, including a BM aspirate clot, and biopsy are required as part of the baseline visit, Day 22 to 28 of Cycle 2, and to confirm CR in subjects negative for blood and urine M-protein. In Part B, Part C, and Part D, BM aspirate and biopsy are also required in Cycle 6 and every 6 cycles thereafter. Both BM aspirate and biopsy samples will be assessed locally at the site for clinical evaluation. In addition, biomarker analyses will be performed centrally on these samples (see Section [7.5](#)). Any additional BM aspirates and biopsies collected at any other time while on the trial may also be submitted for central assessment.

The BM specimens will be tested centrally for assessment of response/resistance to SEA-BCMA and may include but are not limited to: evaluation of BCMA expression, immune activation, disease risk profiling, gene expression profiling, and MRD assessment.

The determination of antitumor activity will be based on response assessments made according to the 2016 IMWG Criteria ([Kumar 2016](#)) (see [Appendix J](#)). Treatment decisions by the investigator will be based on these assessments. Clinical response of stringent complete response (sCR), CR, VGPR, PR, SD, and PD will be determined at each assessment based on local laboratory (and the modified SPEP run by the central laboratory for subjects with IgG MM), radiological, and clinical evaluations. PD is based on IMWG 2016 criteria and/or clinical disease progression per investigator. All IMWG responses must be confirmed responses. When applicable, determination of immunophenotypic CR, MRD status, and minimal response will be made per the IMWG 2016 criteria.

Subjects' clinical data must be available for CRF source verification. Copies of tumor images must be made available for review by the sponsor (or its designee), upon request.

7.3. Qualitative Interviews

Up to a total of 10 subjects in Parts C and D will be interviewed within 1 cycle of the time of first OR (PR or better) or ongoing SD at the end of Cycle 4 (Part C only). See the Interview Guide for additional details.

7.4. Pharmacokinetic and Immunogenicity Assessments

Blood and BM samples for PK and ATA assessment will be collected at time points outlined in [Appendix B](#). In Parts C and D, additional PK samples will be collected and archived for possible analysis of concentrations of combination drugs.

Qualified assays will be used to measure concentrations of SEA-BCMA in serum and BM and ATA in serum. Remaining PK samples will be archived for possible analysis of SEA-BCMA related species. The assays will include enzyme-linked immunosorbent assays (ELISA) assay, as well as other assays if further characterization is required.

A qualified electrochemiluminescence assay will be used to assess ATA.

7.5. Biomarker Studies

Peripheral blood and BM samples for biomarker analyses will be collected at time points outlined in [Appendix B](#). In addition to protocol-mandated collections of tumor specimens, BM specimens collected at the discretion of the investigator may be submitted for central biomarkers analysis. For all BM collections, sites will supply BM aspirates as well as BM biopsy specimens and BM aspirate clot specimens as formalin-fixed, paraffin-embedded (FFPE) blocks. For samples acquired for SOC, unstained slides may be submitted if an FFPE block for the BM biopsy or clot are not available. Samples will be sent to the central lab for analysis as described in the laboratory manual.

Samples will be evaluated for expression of BCMA and relevant biomarkers that may be associated with the activity of SEA-BCMA and/or change in response to treatment. Analysis of tumor tissue and peripheral blood may also include markers associated with prognosis, response, or resistance. Changes in peripheral blood immune cell subsets will be measured as potential pharmacodynamic and safety markers.

7.5.1. Genetic profiling of effector cells

Single nucleotide polymorphisms of Fc γ RIIA and Fc γ RIIIA, which may influence the response to SEA-BCMA, may be determined, including, but not limited to, testing of the following polymorphisms:

- Fc γ RIIIA – 158V/F
- Fc γ RIIA – 131H/R

7.5.2. Serum Free Light Chain and modified SPEP

Kappa and Lambda FLCs will be quantified in serum of subjects as surrogate markers of antitumor activity.

For subjects with IgG myeloma who have low levels of serum M-protein SPEP, a reflex modified SPEP assay will be used to assess for residual serum M-protein in the absence of interference from SEA-BCMA.

7.5.3. Peripheral blood immunophenotyping

Peripheral blood samples will be collected for evaluation of circulating immune cells by flow cytometry. Changes in circulating immune cell subsets will be measured as potential pharmacodynamic markers of SEA-BCMA activity. Flow cytometry measurements will include, but not be limited to, characterizing NK cells, monocytes, T-cells, and B-cells.

7.5.4. Plasma cytokines/chemokines

The levels of circulating cytokines/chemokines may be assessed by ELISA and/or multiplex cytokine/chemokines assays.

7.5.5. Soluble target and ligands

The levels of circulating sBCMA, APRIL and BAFF may be assessed by ELISA or other methods (eg, LC-MS or flow cytometry).

7.5.6. Plasma Biomarkers and PBMCs

Plasma and PBMCs will be collected for retrospective analyses of cellular and circulating biomarkers associated with response and/or resistance to SEA-BCMA.

7.5.7. Characterization of Tumor Tissue

Baseline and on-treatment BM aspirates and biopsies will be collected to assess disease relevant immune subsets, characterize tumor burden, investigate depth of response and determine prognostic signatures and response to treatment. Additional protein, gene expression profiling, as well as further molecular characterization of the tumor for myeloma disease relevant risk markers, may also be evaluated to identify biomarkers predictive of response or resistance to SEA-BCMA.

7.5.7.1. Bone marrow immunophenotyping

Expression of BCMA on tumor plasma cells, as well as presence and changes of immune components in the BM, may be evaluated by flow cytometry and/or immunohistochemistry.

7.5.7.2. Gene Expression Profiling/NGS/FISH

Baseline and treatment-related changes in gene expression profiles in tumor and tumor microenvironment may be assessed by RNA sequencing of tumor (CD138-positive) and nontumor (CD138-negative) cells purified from BM aspirates, to determine prognostic disease-risk signatures as well as baseline characteristics and on-treatment changes that may correlate with response or resistance. Cytogenetic analyses or DNA sequencing of CD138-positive plasma cells enriched from BM aspirate collected at Baseline may also be carried out to further determine genetic changes that may predict or be associated with response to SEA-BCMA.

7.5.7.3. MRD

MRD evaluation using the Adaptive next generation sequencing (NGS) for MRD assay ([Martinez-Lopez 2014](#)) may be carried out on relevant specimens to understand the activity of SEA-BCMA.

7.5.7.4. Bone marrow plasma

BM plasma will be collected and may be tested for levels of soluble target, ligands, and/or cytokines/chemokines that may influence or correlate with response to SEA-BCMA.

7.6. Biospecimen Repository

In the US only, for subjects who provide additional consent, remaining de-identified unused blood and/or tissue will be retained by Seagen and used for future research, including but not limited to the evaluation of targets for novel therapeutic agents, the biology of sensitivity and

resistance mechanisms to SEA-BCMA, and the identification of biomarkers of MM disease and response/resistance to therapy. Blood, BM, and tissue samples donated for future research will be retained for a period of up to 25 years. If additional consent is not provided, any remaining biological samples will be destroyed after the study has been completed and all applicable regulatory obligations have been met.

7.7. Safety Assessments

The assessment of safety during the course of this study will consist of the surveillance and recording of AEs including SAEs, recording of concomitant medication, and measurements of protocol-specified physical examination findings and laboratory tests.

Safety will be monitored as described in Section 9.3.9 over the course of the study by the SMC.

7.7.1. Adverse Events

7.7.1.1. Definitions

Adverse Event

According to the International Council for Harmonisation (ICH) E2A guideline Definitions and Standards for Expedited Reporting, and 21 CFR 312.32, IND Safety Reporting, an AE is any untoward medical occurrence in a subject or clinical investigational subject administered a medicinal product and which does not necessarily have a causal relationship with this treatment.

The following information should be considered when determining whether or not to record a test result, medical condition, or other incident on the Adverse Events CRF:

- From the time of informed consent through the day prior to study Day 1, only study protocol-related AEs should be recorded. A protocol-related AE is defined as an untoward medical event occurring as a result of a protocol-mandated procedure.
- All medical conditions present or ongoing predose on study Day 1 should be recorded.
- All AEs (regardless of relationship to study drug) should be recorded from study Day 1 predose through the end of the safety reporting period (see Section 7.7.7). Complications that occur in association with any procedure (eg, biopsy) should be recorded as AEs whether or not the procedure was protocol-mandated.
- Changes in medical conditions and AEs, including changes in severity, frequency, or character, during the safety reporting period should be recorded.
- In general, an abnormal laboratory value should not be recorded as an AE unless it is associated with clinical signs or symptoms, requires an intervention, results in a SAE, or results in study termination or interruption/discontinuation of study treatment. When recording an AE resulting from a laboratory abnormality, the resulting medical condition rather than the abnormality itself should be recorded (eg, record “anemia” rather than “low hemoglobin”).

7.7.2. Serious Adverse Events

An AE should be classified as an SAE if it meets one of the following criteria:

Fatal:	AE resulted in death
Life threatening:	The AEs placed the subject at immediate risk of death. This classification does not apply to an AE that hypothetically might cause death if it were more severe.
Hospitalization:	The AE resulted in hospitalization or prolonged an existing insubject hospitalization. Hospitalizations for elective medical or surgical procedures or treatments planned before the signing of informed consent in the study or routine check-ups are not SAEs by this criterion. Admission to a palliative unit or hospice care facility is not considered to be a hospitalization. Hospitalizations or prolonged hospitalizations for scheduled therapy of the underlying cancer or study target disease need not be captured as SAEs.
Disabling/incapacitating:	An AE that resulted in a persistent or significant incapacity or substantial disruption of the subject's ability to conduct normal life functions.
Congenital anomaly or birth defect:	An adverse outcome in a child or fetus of a subject exposed to the molecule or study treatment regimen before conception or during pregnancy.
Medically significant:	The AE did not meet any of the above criteria but could have jeopardized the subject and might have required medical or surgical intervention to prevent one of the outcomes listed above or involves suspected transmission via a medicinal product of an infectious agent. Potential drug-induced liver injury (DILI) also is considered a medically significant event (see Section 7.7.3.2 for the definition of potential DILI)

AE = adverse event, DILI = drug-induced liver injury, SAE = serious adverse event

7.7.3. Adverse Event Severity

AE severity should be graded using the NCI-CTCAE, v. 4.03. These criteria are provided in the study manual.

AE severity and seriousness are assessed independently. 'Severity' characterizes the intensity of an AE. 'Serious' is a regulatory definition and serves as a guide to the sponsor for defining regulatory reporting obligations (see definition for SAEs above).

7.7.3.1. Relationship of the Adverse Event to Study Treatment

The relationship of each AE to each study treatment (SEA-BCMA, and/or dexamethasone, and/or pomalidomide) should be evaluated by the investigator using the following criteria:

Related:

There is evidence to suggest a causal relationship between the drug and the AE, such as:

- A single occurrence of an event that is uncommon and known to be strongly associated with drug exposure (eg, angioedema, hepatic injury, Stevens-Johnson Syndrome)
- One or more occurrences of an event that is not commonly associated with drug exposure, but is otherwise uncommon in the population exposed to the drug (eg, tendon rupture)

Unrelated:

Another cause of the AE is more plausible (eg, due to underlying disease or occurs commonly in the study population), or a temporal sequence cannot be established with the onset of the AE and administration of the study treatment, or a causal relationship is considered biologically implausible

7.7.3.2. Procedures for Eliciting and Recording Adverse Events

Investigator and study personnel will report all AEs and SAEs whether elicited during subject questioning, discovered during physical examination, laboratory testing and/or other means by recording them on the CRF and/or SAE form, as appropriate.

Eliciting Adverse Events

An open-ended or nondirected method of questioning should be used at each study visit to elicit the reporting of AEs.

Recording Adverse Events

The following information should be recorded on the Adverse Events CRF:

- Description including onset and resolution dates
- Whether it met SAE criteria
- Severity
- Relationship to study treatment or other causality
- Outcome

Diagnosis vs Signs or Symptoms

In general, the use of a unifying diagnosis is preferred to the listing out of individual symptoms. Grouping of symptoms into a diagnosis should only be done if each component sign and/or symptom is a medically confirmed component of a diagnosis as evidenced by standard medical textbooks. If any aspect of a sign or symptom does not fit into a classic pattern of the diagnosis, report the individual symptom as a separate AE.

Adverse reactions associated with the infusion of study drug may occur in this study. For IHRs, record the NCI-CTCAE terms of ‘infusion-related reaction,’ ‘allergic or hypersensitivity reaction,’ ‘cytokine release syndrome,’ or ‘anaphylaxis’ with an overall level of severity (per

NCI-CTCAE v. 4.03). In addition, record each sign or symptom of the reaction as an individual AE. If multiple signs or symptoms occur with a given infusion-related event, each sign or symptom should be recorded separately with its level of severity.

Recording Serious Adverse Events

For SAEs, record the event(s) on both the CRF and an SAE form.

The following should be considered when recording SAEs:

- Death is an outcome of an event. The event that resulted in the death should be recorded and reported on both an SAE form and CRF.
- For hospitalizations, surgical, or diagnostic procedures, the illness leading to the surgical or diagnostic procedure should be recorded as the SAE, not the procedure itself. The procedure should be captured in the narrative as part of the action taken in response to the illness.

7.7.4. Progression of the Underlying Malignancy

Since progression of underlying malignancy is being assessed as an efficacy variable, it should not be reported as an AE or SAE. The terms “Disease Progression”, “Progression of Disease” or “Malignant disease progression” and other similar terms should not be used to describe an AE or SAE. However, clinical symptoms of progression may be reported as AEs or SAEs if the symptom cannot be determined as exclusively due to progression of the underlying malignancy or does not fit the expected pattern of progression for the disease under study. In addition, complications from progression of the underlying malignancy should be reported as AEs or SAEs.

7.7.5. Pregnancy

7.7.5.1. Notification to Drug Safety

Complete a Pregnancy Report Form for all pregnancies that occur from the time of first study drug dose until 6 months after the last dose of study drug(s) including any pregnancies that occur in the partner of a study subject who is able to father a child. Only report pregnancies that occur in a subject's partner if the estimated date of conception is after the subject's first study drug dose. Email or fax to the sponsor's Drug Safety Department within 24 hours of becoming aware of a pregnancy. As part of the study, all pregnancies will be monitored for the full duration and all perinatal and neonatal outcomes should be reported. Infants should be followed for a minimum of 8 weeks.

7.7.5.2. Collection of data on the CRF

All pregnancies (as described above) that occur within 30 days of the last dose of study drug(s) will also be recorded on the Adverse Events CRF.

Abortion, whether accidental, therapeutic, or spontaneous, should be reported as an SAE. Congenital anomalies or birth defects, as defined by the ‘serious’ criterion above (see definitions Section 7.7.1.1) should be reported as SAEs.

7.7.6. Potential Drug-Induced Liver Injury

The observation of the critical importance of altered liver function has been referred to informally as Hy’s Law ([Reuben 2004](#)). Hy’s Law can be used to estimate severity and the likelihood that a study drug may cause an increased incidence of severe hepatotoxicity.

The absence of hepatotoxicity in clinical trials provides a limited predictive value for potential hepatotoxicity in the clinical setting(s) being studied. However, finding 1 Hy’s Law case in clinical trials is ominous; finding 2 cases is highly predictive of a potential for severe DILI.

7.7.6.1. Definition

Briefly, potential Hy’s Law cases include the following 3 components:

1. Aminotransferase (ALT and/or AST) elevation $>3 \times$ ULN
AND
2. Total bilirubin $>2 \times$ ULN, without initial findings of cholestasis (ie, elevated serum alkaline phosphatase),
AND
3. No other immediately apparent possible causes of aminotransferase elevation and hyperbilirubinemia, including, but not limited to, viral hepatitis, pre-existing chronic or acute liver disease, or the administration of other drug(s) known to be hepatotoxic.

7.7.6.2. Reporting Requirements

Any potential Hy’s Law case should be handled as an SAE associated with the use of the drug and reported promptly to the Sponsor.

Reporting should include all available information and should initiate close follow-up until complete resolution of the problem and completion of all attempts to obtain supplementary data.

7.7.6.3. Follow-up for Abnormal Laboratory Results Suggesting Potential DILI

In general, an increase of serum ALT or AST to $>3 \times$ ULN should be followed by repeat testing within 48 to 72 hours of serum ALT, AST, alkaline phosphatase, and total bilirubin, to confirm the abnormalities and to determine whether they are worsening.

Appropriate medical assessment should be initiated to investigate potential confounding factors and alternative causes of hepatotoxicity. During this investigation, study drug should be withheld.

Regional guidelines should be followed. Additional information is provided in FDA Guidance for Industry, DILI: Premarketing Clinical Evaluation, 2009 and Health Canada Guidance Document; Pre-market Evaluation of Hepatotoxicity in Health Products, 2012.

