In intensive dosing weekly induction Cycles 1 and 2, if a subject has a clinically significant, unresolved AE that prevents dosing on Day 8, 15, or 22, the dose may be delayed for ≤ 3 days. On the third day, if a subject cannot receive the dose, the dose of SEA-BCMA will be eliminated and the corresponding visit will be skipped; dosing and visit schedule would resume the following week (eg, at Day 22, if Day 15 is skipped). However, if a Day 8, 15, or 22 dose is delayed for ≤ 3 days, subsequent study assessments within the same cycle will be delayed by the same number of days as the dose delay, and study drug administration for the next dose will be delayed by at least the same number of days.

During the DLT period (Cycle 1), growth factor and transfusion support is discouraged unless medically indicated; subjects who receive growth factor (eg, granulocyte colony-stimulating factor or granulocyte-macrophage colony-stimulating factor) or transfusion support (other than

red blood cell transfusions for MM-related anemia) during this period for reasons other than DLT may not be evaluable for DLT, except in Part D, where granulocyte colony-stimulating factor is permitted during Cycle 1 if given as primary or secondary prophylaxis in conjunction with pomalidomide. Consideration should be given for growth factor support for prophylaxis or treatment of cytopenias in subsequent cycles (Table 5). During dose-escalation, subjects with Grade 4 neutropenia must have a follow-up complete blood count (CBC) with differential obtained 5 days from the time of assessment for evaluation of DLT. In addition, subjects with Grade 3 asymptomatic laboratory abnormalities must have follow-up laboratory evaluation obtained 72 hours from the time of assessment for evaluation of DLT. Serum chemistry and CBCs should be collected minimally on a weekly schedule during dose delays resulting from toxicity.

Table 5 describes the recommended dose modifications for toxicity.

Table 5: Recommended dose modifications for toxicity

Toxicity	Grade 1	Grade 2	Grade 3	Grade 4
Nonhematologic (AE or laboratory abnormality)	Continue at same dose level	Continue at same dose level	Withhold dose until toxicity is \leq Grade 1 or baseline ^a , and then resume treatment at 50% of the SEA-BCMA dose	Discontinue study treatment

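### For ALT or AST above 3 x ULN but below Grade 3, Protocol Section 7.7.6.3 says to hold study drug while Table 5 recommends continuing, and nothing reconciles the two

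*Protocol*

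**What the plan says.** Protocol Section 7.7.6.3 opens "In general, an increase of serum ALT or AST to" more than 3 x ULN, and says such a rise "should be followed by repeat testing within 48 to 72 hours of serum ALT, AST, alkaline phosphatase, and total bilirubin". It continues: "Appropriate medical assessment should be initiated to investigate potential confounding factors and alternative causes of hepatotoxicity". Then comes the dosing instruction: "During this investigation, study drug should be withheld". The stated trigger is the aminotransferase value alone. No CTCAE grade is attached, and the bilirubin condition belongs to the Hy's Law definition in Section 7.7.6.1.

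Protocol Section 5.2.3, Table 5, has a row whose label begins "Nonhematologic (AE or laboratory abnormality". For Grade 1 and for Grade 2 the entry is "Continue at same dose level". At Grade 3 the dose is withheld until the toxicity has settled, "and then resume treatment at 50% of the SEA-BCMA dose". At Grade 4 study treatment is discontinued. The only toxicity that the table sends elsewhere is the infusion-related reaction, to Section 5.7.1.

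The SAP has no rule on this point.

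**The concern.** A subject whose ALT or AST is above 3 x ULN but not yet Grade 3 meets both instructions. One says hold during the work-up; the other recommends continuing. Neither passage refers to the other, and no sentence says which takes precedence. This is a hepatic-safety instruction, so the first thing at stake is that subjects with the same signal are handled consistently.

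The second is the data behind the primary endpoints. Under Section 7.7.1.1 an abnormal laboratory value is generally not recorded as an AE unless, among other conditions, it leads to interruption of study treatment. An otherwise unremarkable value could therefore become an AE where the dose is held and not where it is continued. In Cycle 1 a hold can also bear on DLT status or on the share of the intended dose received. The run-ins turn on 0 or 1 against 2 or more DLTs in 6 subjects (Sections 3.1.2 and 3.1.3.2; Part D uses the same limit in Section 3.1.3.3), so one subject classified differently can matter.

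**Working it through.** The plan states no figure to reproduce. The check compares the passages and adds simple arithmetic.

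**1. Do the two instructions meet?** Section 7.7.6.3 applies above 3 x ULN. Table 5 gives the same entry for Grades 1 and 2, so only the lower bound of Grade 3 matters. Grading is by CTCAE v4.03 (Section 7.7.3), whose ALT/AST cut-offs the documents do not print. The bound is therefore an assumption:

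Width of overlap = (Grade 3 lower bound) − 3, in multiples of ULN, and zero if negative.

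| Assumed Grade 3 lower bound | Overlap | Width |
|---|---|---|
| 3 x ULN or below | none | 0 |
| 4 x ULN | >3 to 4 | 4 − 3 = 1 |
| 5 x ULN | >3 to 5 | 5 − 3 = 2 |
| 6 x ULN | >3 to 6 | 6 − 3 = 3 |

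From Grade 3 upward both passages stop dosing, so the direct conflict is confined to this zone. Exclusion criterion 16b bars ALT or AST above 3 x ULN at entry, so values in the zone are on-study rises. The documents give no incidence for them.

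**2. Which text would a site reach?** The Day 1 instructions for all four parts (Sections 6.2.3.1, 6.3.3.1, 6.4.3.1 and 6.5.3.1) send sites to Sections 5.2.3 and 5.7.1 for dose modifications in later cycles. Section 7.7.6.3 is not named. The SAE table in Section 7.7.2 refers to Section 7.7.3.2 for the definition of potential DILI, but that section covers AE recording; the definition is in Section 7.7.6.1.

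**3. Does Table 5 deal with withholding at all?** Yes. Its Grade 3 entry withholds expressly, and its Grade 1 and 2 entries do not. The table is not silent on the matter.

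**4. What could a hold do to Cycle 1?** The inputs are 4 planned Cycle 1 doses on the weekly schedule and 2 on q2wk (Section 3.1, Figure 1); a 75% minimum of the intended Cycle 1 dose for a subject without a DLT (Protocol Section 9.3.1.7.3; SAP Section 4.2); and a toxicity delay of more than 7 days counted as a DLT (Section 3.1.5).

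Share received = (planned − lost) / planned.

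- Weekly, one lost: (4 − 1)/4 = 75%, which just meets the minimum.
- Weekly, two lost: (4 − 2)/4 = 50%, below it.
- q2wk, Day 15 lost: (2 − 1)/2 = 50%, below it.

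**5. Must a hold cost a dose?** No. On the weekly schedule a Day 8, 15 or 22 dose may be delayed up to 3 days. After that, "On the third day, if a subject cannot receive the dose, the dose of SEA-BCMA will be eliminated". On q2wk the Day 15 allowance is 7 days. A retest at 48 to 72 hours (2 to 3 days) can fit inside either allowance. A dose is lost only if the hold outlasts the allowance, for example because the cause investigation is still open.

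**6. Which drugs are held?** Section 7.7.6.3 says only study drug. In Part C that could include dexamethasone, and in Part D pomalidomide as well. Table 7 already gives pomalidomide its own liver-enzyme rule, from Grade 1 upward.

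**The case against.** The best defence is that the passages can be read together. Table 5 can be taken to set the dose level, and Section 7.7.6.3 to add a temporary pause while possible DILI is investigated, after which dosing resumes at the same level. Section 7.7.6.3 is the more specific text, and its heading confines it to results suggesting potential DILI. Both texts are soft: one is framed as general guidance, the other as recommendations. Section 5.2.3 also lets an investigator delay a dose for a clinically significant unresolved AE, with no grade threshold.

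That reading is possible, but the protocol does not state it. The only trigger given in Section 7.7.6.3 is the enzyme value, Table 5 withholds at Grade 3 and not below, and the delay provision permits a hold without requiring one.

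The defence does succeed against several stronger readings that a reader might infer:

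- **That sites will in fact dose differently.** The documents show only that they can. DLT determination and run-in recommendations go through the SMC (Section 3.1.9.2), not site by site.
- **That a subject handled under Table 5 receives 100% of the dose.** Section 5.2.3 allows delays, so this is not assured.
- **That the retest itself costs a weekly dose.** It can be completed within the 3-day allowance, and the hold is worded around the cause investigation rather than the retest alone.
- **That two lost weekly doses mean replacement.** If the toxicity delay exceeds 7 days it is a DLT, and a subject with a DLT is evaluable whatever dose was received.

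**Conclusion.** The point holds as an unreconciled conflict between two soft instructions for one defined situation: ALT or AST above 3 x ULN and below Grade 3. It is more than missing detail, because the texts point in opposite directions on a hepatic-safety action and the visit instructions lead to only one of them. Its extent rests on the assumed Grade 3 bound: >3 to 5 x ULN if that bound is 5, narrower at 4, wider at 6, and none at 3 or below. How often it would arise cannot be judged from the documents.

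The effect on Cycle 1 data is conditional. A reader might infer that DLT-evaluability is left undefined for a held dose. The documents do not support that: the 75% minimum, the 7-day delay criterion and, in SAP Section 4.2, the SMC's power to deem a subject inevaluable already cover it. No view is taken on which dosing instruction is right.

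**What to change.** Reconcile Section 7.7.6.3 and Table 5 so that they give one instruction for ALT or AST above 3 x ULN and below Grade 3. A liver-enzyme row in Table 5, or a cross-reference from Table 5 to Section 7.7.6.3 that states precedence, would do it. In the same edit, state which agents study drug covers in Section 7.7.6.3 for Parts C and D, and how that sits with the pomalidomide rule in Table 7. No separate evaluability rule is needed. The cost is protocol wording only; no sample size, analysis set or endpoint changes.
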